15. APPENDICES
 - a. Appendix-1: Informed Consent Form (ICF)

LIST OF ABBREVIATIONS

FDA- Food and drug administration

AGA- Androgenetic alopecia

1. STUDY OBJECTIVES:

Evaluate the effect of the topical herbal solution on the prevention and treatment of androgenetic alopecia and comparison with 5% minoxidil

2. STUDY DESIGN

This study will be done on male patients with androgenic hair loss. The patients will be selected by volunteers attending the Dermatology department of Sina Hospital and eligible individuals will be selected among them. The participants will be randomly allocated (using random number tables) to two groups; the first group will receive a 5% minoxidil topical solution, and the second group will receive a 5% minoxidil topical solution plus the topical herbal solution for 36 weeks. The hair thickness will be measured to determine efficacy at baseline, 12, 24, and 36 weeks. The patient's questionnaire self-evaluation and side effects will also be evaluated.

3. BACKGROUND AND RATIONALE

Androgenetic alopecia (AGA) is mostly caused by miniaturization of androgen-sensitive hair follicles and common form of scalp hair loss. AGA can affect the quality of life, self-confidence, and change in interpersonal and social relationships, especially among young people. AGA can be capable of affecting all races. The highest prevalence is observed in Caucasians. Finasteride and Minoxidil have been approved by the American Food and Drug Administration (FDA) for the treatment of AGA. Conventional therapy has many side effects. Herbal remedies can be more advancing than conventional when used topically on the scalp. Herbal remedies characterized by patient satisfaction, fewer side effects, and more mechanism in the treatment of AGA.

4. STUDY POPULATION

4.1 Inclusion criteria

- Men 18 to 50 years old
- Written consent
- Normal general health status
- Men who have a presentation of androgenetic alopecia (Norwood II - V).

4.2 Exclusion criteria

- Used any of topical product in the target region interfering with the study product in the last 12 months
- Within the past six months receiving of chemotherapy/cytotoxic agents
- Clinical diagnosis of alopecia areata or other non-AGA forms of alopecia

- Uncontrolled hypertension
- Any dermatological disorders in the scalp, such as fungal or bacterial infections, eczema, atopic dermatitis, seborrheic dermatitis, psoriasis, sun damage, skin cancer
- Hormonal diseases, such as thyroid disorders and diabetes.
- Smokers
- Liver and kidney disease
- History of hair transplants
- History of surgical correction of hair loss on the scalp
- Subject having dyed, bleached hair, or with a permanent wave before study start.
- No written consent

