4.3 Criteria for terminating study participation

- Subject wishes to stop being in the study
- Subjects are not eligible based on inclusion/exclusion criteria
- Adverse events occur that, in the opinion of the investigator, but the subject at increased risk and it is not in the best interest of the subject to continue the study

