5. STUDY PROCEDURES

5.1 Screening visit

- Subjects who meet the inclusion/exclusion criteria will be enrolled, and written informed consent will be obtained.
- The subject's demographic data, medical history, duration and onset of AGA, and current usage of any topical or systemic drug for the treatment of AGA will be recorded.

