5.2 Treatment Visit

- In addition to oral explanations, participants will be given written instructions on how to use solutions and storage conditions.
- Subjects will not be permitted to apply their usual hair cosmetics products and will be requested not to alter their usual routine hair care during the study period.
- Subjects will be instructed to avoid the use of any prescribed and/or nonprescription therapeutic agents for preventing hair loss or hair growth during the study period.
- Baseline hair thickness will be taken, and every three months, it will be repeated. For reproducibility, the target location on the scalp, where the hair thickness will be measured over time, consist of Intersecting three distances from the fixed anatomical locations.

Treatment randomization

Before the study begins, a random number table will be generated (in 1:1 ratio) for each study participant according to the subject number. The number will indicate whether treatment or control will be taken on the study groups. “0” represents a 5% minoxidil topical solution whereas “1” represents a 5% minoxidil topical solution plus the topical herbal solution.

Blinding

Dermatologist and the randomized subjects will be blinded to the subject’s allocation. It is necessary to use blinded treatment in order to reduce potential bias during data collection and evaluation of study outcomes.

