6. DATA COLLECTION AND REPORTING

6.1 Primary Outcome Measures

Hair thickness via a digital micrometer will record for each subject by a blinded investigator at the treatment visit (before treatment) and during the three months, six months, and 9-month follow-up visits.

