11. STATISTICAL ANALYSIS PLAN (SAP)

The statistical analysis will be performed using SPSS software 25 (SPSS Inc., Chicago, IL, USA). The normalcy of continuous data will be checked using the Kolmogorov-Smirnov Test. Mean (SD) will be calculated for all normally distributed continuous variables, e.g., age, duration of disease, hair diameter, etc. The unpaired (independent) t-test and paired t-test will be applied to compare the mean of hair diameter between two study groups and within

groups, respectively. For differences between self-assessment questionnaires, the Mann-Whitney test will be performed. At or before the time of the Week 0 administration, subject demographics, hair diameter, and duration of AGA will be summarized. All statistical tests will be two-side and will perform at a significance level of p -value < 0.05 .

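### Do the planned hair-diameter analyses go wrong because eligibility is silent on current systemic AGA drug use?

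*Combined protocol and SAP*

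**What the plan says.** The following places in the combined protocol and SAP bear on the point.

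- **Section 4.2, Exclusion criteria.** The only exclusion for earlier hair treatment concerns topical products: "Used any of topical product in the target region interfering with the study product in the last 12 months". The chemotherapy/cytotoxic exclusion in the same list does not reach AGA drugs. Section 3 names finasteride as an approved treatment, so the authors knew of drugs other than minoxidil.
- **Section 5.1, Screening visit.** Among the items collected, "current usage of any topical or systemic drug for the treatment of AGA will be recorded". No consequence of a positive answer is stated, and past use and stopping dates are not mentioned.
- **Section 4.3, Criteria for terminating study participation.** One ground is that "Subjects are not eligible based on inclusion/exclusion criteria", which points back to the same list.
- **Section 5.2, Treatment Visit.** Subjects are told to "avoid the use of any prescribed and/or nonprescription therapeutic agents for preventing hair loss or hair growth during the study period". No drug-free interval before baseline is given. Section 6.1 places the baseline measurement at the treatment visit, before treatment starts.
- **Section 11, SAP.** At baseline, "subject demographics, hair diameter, and duration of AGA will be summarized"; AGA drug use is not in the list. Hair diameter is compared between groups by the unpaired t-test and within groups by the paired t-test, with no covariate or sensitivity analysis.
- **Section 1, Study objectives.** The aim includes "comparison with 5% minoxidil", which is the randomised contrast.

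**The concern.** Read in sequence, these sections permit an awkward case. A man on a systemic AGA drug meets every written criterion, has his use noted, is measured at baseline while the drug is acting, and is then told to use no hair-loss agents for 36 weeks. If stopping changes hair diameter, his change from baseline mixes that effect with the effect of the study solution.

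The paired t-test is a planned analysis of the primary outcome, and randomisation gives it no protection. With enough such men in an arm, a test run at 5% could reject much more often when the study treatment does nothing, or could miss a real gain. The one variable that would reveal this is collected but given no role in Section 11, so a report that followed Section 11 to the letter would not show how many users were in each group.

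**Working it through.** The documents provided give no sample size, SD, effect size, share of users or withdrawal effect, so there is no planned figure to reproduce. The calculation below shows orders of magnitude only.

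**Assumed inputs**
- f, the share of men in an arm who stop a systemic AGA drug at entry: 0.1 to 0.3.
- k, the mean shift on stopping, in SDs of baseline-to-follow-up change among non-users: 0.25 to 1.0.
- n = 30 per arm.

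The two-sided 5% level is from Section 11.

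**Within-group paired test**

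Bias in mean change = f·k. Variance ratio = 1 + f(1−f)k². Rejection rates come from the noncentral t with 29 degrees of freedom and noncentrality f·k·√n / √(variance ratio).

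| f | k | Bias (SD) | Variance ratio | Rejection, no study effect | Power for a true 0.5 SD gain if the shift is a loss |
|---|---|---|---|---|---|
| 0 | – | 0 | 1 | 5% | 75% |
| 0.1 | 0.25 | 0.025 | 1.0056 | 5.2% | 71% |
| 0.1 | 0.5 | 0.05 | 1.0225 | 5.8% | 65% |
| 0.3 | 1.0 | 0.30 | 1.21 | 30% | 16% |

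For the last row, the noncentrality is 0.30 × √30 / √1.21 = 1.49.

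Direction matters. If the shift is a loss, nearly all of the 30% lies in the tail for thinning. The rate of false gains falls from 2.5% to about 0.03%.

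**Between-group comparison**

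Randomisation gives both arms the same expected share of users, so the expected difference due to stopping is f·k − f·k = 0. In simulations with no treatment effect (20,000 runs per setting), the unpaired t-test rejected in 4.9% to 5.2% of runs. What remains is extra variance.

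- *Change scores, constant shift.* Standard error ratio = √(1 + f(1−f)k²), from √1.0056 = 1.003 to √1.21 = 1.10.
- *Change scores, shift varying between men with SD half its mean.* At f = 0.3 and k = 1: √(1 + 0.21 + 0.3 × 0.25) = √1.285 = 1.13.
- *Raw follow-up diameter, which is how Section 11 reads.* If users end lower than non-users by the shift, and ρ is the baseline/follow-up correlation with equal variances, the ratio is √(1 + f(1−f)k²·2(1−ρ)). At f = 0.3 and k = 1 this is 1.04 for ρ = 0.8, 1.10 for ρ = 0.5 and 1.14 for ρ = 0.3. If users have returned to the non-user level, it is 1.00.

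The between-group cost is therefore roughly 0% to 14% in standard error, with the upper end reached only at 30% users and a full 1.0 SD shift.

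**What a covariate would buy**

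At k = 0.25, nothing. At f = 0.3 and k = 1, the standard error ratio goes from about 1.10 to about 1.01. At f = 0.1 the expected number of users is 30 × 0.1 = 3 per arm, and the binomial chance of fewer than 3 in an arm is 41%, so the term would often rest on one or two men. A covariate in the between-group model does not touch the paired tests.

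**The case for a change.** The best argument for a change is that it is cheap and the text does not close the gap. The on-study ban in Section 5.2 does not rescue the baseline: it is the instruction that makes a current user stop, and with no interval stated his baseline can be measured under the drug. Section 4.3 cannot remove him, because it refers to criteria that he meets. One sentence on eligibility would stop staff applying different unwritten rules, and one table row would show readers how many users were in each arm.

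All of that is accurate about the text. What it does not show is a fault in the planned inference. The documents leave eligibility of systemic users open; they do not show that such men are meant to be enrolled. For harm to follow, current users would have to volunteer, be accepted after their use has been noted, stop at entry, and change in hair diameter as a result, in numbers that matter. Even then the damage falls on paired tests that already absorb every other change over time and could not by themselves establish efficacy. Removing this one source would not turn them into evidence of a treatment effect.

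The analytic additions are weaker still. Each depends on a decision not yet taken, namely that users may enrol. A between-group covariate or exclusion analysis would address a comparison that is already unbiased.

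**Conclusion.** The omission stands as a matter of text: Sections 4.2, 5.1 and 5.2 do not settle whether current systemic AGA drug users may enrol or how time off such a drug relates to baseline, and Section 11 does not mention the recorded item. It is a gap that those running and analysing the trial can fill sensibly. The eligibility rule is the sponsor's to set, and this review takes no position on it. If any users do enrol, showing them by group in the baseline table, and looking at the paired changes without them, are ordinary steps that use data already collected under Section 5.1. That covers current users only, since past use is not named there.

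The comparison that answers the study objective is unbiased in expectation, holds its 5% level, and loses somewhere between nothing and about 14% in standard error. The paired tests could be distorted by 0.025 to 0.30 SD of change, and if stopping causes a loss the distortion works against showing a gain in either arm. Every one of these sizes rests on an assumed share of users, shift, arm size or correlation. At the milder settings (10% users, a shift of 0.5 SD or less) the paired test rejects 5.2% to 5.8% of the time, close to nominal. No change to the plan is called for.

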4.4 Recruiting/Screening

- The dermatologist will select subjects presenting to the Department of Dermatology Clinic at the Sina hospital who meet the inclusion criteria. Those expressing an interest to participate in the study will contact for a verbal explanation of the protocol by an investigator.
- Written announcements for participation in the study will also be posted on the internet and around the Tabriz University of Medical Sciences, School of Medicine, School of Pharmacy, and School of Dentistry. Volunteer participants will come for a screening visit. If they meet inclusion/exclusion criteria, the participant will consent.
- Consent for participation will be obtained in writing by signature on a consent form by the study staff. Before consent, the consent will be read by the subject, and the subject will be encouraged to ask any questions for clarification. A copy of the subject's signed consent form will be retained in the study file.

4.3 Criteria for terminating study participation

- Subject wishes to stop being in the study
- Subjects are not eligible based on inclusion/exclusion criteria
- Adverse events occur that, in the opinion of the investigator, but the subject at increased risk and it is not in the best interest of the subject to continue the study

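### Men withdrawn for adverse events are no longer measured, and section 11 names only plain t-tests for hair diameter, with no baseline adjustment or as-randomised analysis set

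*Combined protocol and SAP*

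**What the plan says.** Section 4.3 lists the reasons for which a man's participation ends. The adverse-event item has two parts. One concerns risk: "Adverse events occur that, in the opinion of the investigator, but the subject at increased risk". The other concerns whether he should carry on: "it is not in the best interest of the subject to continue the study". What stops is the study; stopping treatment alone is not described.

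The measurement schedule appears in several places. Section 2 says "The hair thickness will be measured to determine efficacy at baseline, 12, 24, and 36 weeks". Section 5.2 says "Baseline hair thickness will be taken, and every three months, it will be repeated". Section 6.1 says "Hair thickness via a digital micrometer will record for each subject by a blinded investigator". Section 5.3 covers visits at 3, 6 and 9 months. None of these has an early-termination visit or a measurement once participation has ended. Section 10 deals with care of adverse events and telephone contact, not with outcome measurement.

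On treatment, section 2 says "the second group will receive a 5% minoxidil topical solution plus the topical herbal solution for 36 weeks". The comparator arm receives minoxidil alone.

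For hair diameter, section 11 says "The unpaired (independent) t-test and paired t-test will be applied to compare the mean of hair diameter between two study groups and within"; the sentence ends by giving the paired test to each arm's own comparison. The only other comparison is for the questionnaire: "For differences between self-assessment questionnaires, the Mann-Whitney test will be performed". Section 11 does not name the visit to be tested, choose between raw value and change, adjust the between-arm test for baseline, define an analysis set or give a missing-data method.

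**The concern.** Hair diameter is the primary outcome and is followed for 36 weeks. A man withdrawn under 4.3 has no later values, and a t-test at a later visit leaves him out. If the men who leave differ in outcome from those who stay, and leave unequally from the two arms, the test no longer compares the randomised groups. Unequal leaving is conceivable because only one arm applies an added product.

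Two further points do not depend on what causes the loss. The choice between raw value and change decides which pattern of loss does harm, and the plan leaves it open. Baseline diameter is already collected but does not enter the between-arm test as a covariate, which costs precision even if nobody leaves.

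**Working it through.** **Text.** Section 6.1 refers to each subject and section 5.2 to a three-monthly repeat. Both set a schedule; neither says that a man whose participation has ended still attends. Sections 2, 5.2, 5.3 and 6.1 therefore do not override 4.3.

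**Inputs.** The documents give 1:1 allocation (5.2), measurement at baseline and weeks 12, 24 and 36 (section 2), and a two-sided 0.05 level (section 11). They give no sample size, SD or loss rate, so there is no planned figure to reproduce. The following are assumptions: 30 men per arm, correlation 0.7 between any two visits, no true effect, and 20% loss in one arm (half after week 12, half after week 24). Bias is in SDs of raw diameter, in favour of the arm that loses men.

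**Formula.** With share d lost from one arm, bias = d × (mean of stayers − mean of leavers). Losing exactly the lowest-diameter men gives a gap of about 1.23 SD at week 36, so 0.20 × 1.23 = 0.246 SD.

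**Simulated bias (type I error in brackets).**

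| Loss (20%, one arm unless stated) | Raw t-test | Change t-test | Baseline-adjusted, completers | All-visit model |
|---|---|---|---|---|
| Random | 0.00 (5%) | 0.00 | 0.00 | 0.00 |
| Exactly the lowest diameters | 0.24 to 0.25 (16% to 17%) | 0.00 (5%) | 0.08 | 0.00 |
| Leaving score correlated 0.5 with diameter | 0.13 (8%) | 0.00 | 0.04 | not run |
| Leaving score correlated 0.3 | 0.08 (6%) | 0.00 | 0.02 | not run |
| Exactly the lowest diameters, both arms | 0.00 (7%) | 0.00 | 0.00 | 0.00 |
| Exactly the poorest changers | 0.00 (6%) | 0.14 (10% to 11%) | 0.10 | 0.00 |
| Exactly the lowest next, unseen values | 0.32 (25%) | not given | 0.16 | 0.13 |

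**Why raw and change swap places.** Let Y0, Y12 and Y36 be the diameters. If selection is on Y12, Cov(Y36, Y12) = 0.7 but Cov(Y36 − Y0, Y12) = 0.7 − 0.7 = 0. If selection is on Y12 − Y0, Cov(Y36, Y12 − Y0) = 0.7 − 0.7 = 0 but Cov(Y36 − Y0, Y12 − Y0) = 0.7 − 0.7 − 0.7 + 1 = 0.3. The exact zeros need equal correlations between visits.

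**Sensitivity, raw t-test, exactly the lowest diameters leaving.** Loss of 10% vs 0% gives 0.13 SD (type I error 10%); 20% vs 10% gives 0.11 SD (9%). At 20% vs 0%, correlation 0.5 gives 0.18 SD and 0.9 gives 0.31 SD. A simpler calculation at 20% vs 5%, with gaps of 0.25 to 1.0 SD, gives 0.15 × 0.25 = 0.04 to 0.15 × 1.0 = 0.15 SD.

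**Continued measurement with some men still lost.** In the unseen-value case the stayers' mean is 0.318. The leavers' mean L satisfies 0.8 × 0.318 + 0.2 × L = 0, so L = −1.272. If half the leavers are still lost, the 90% measured have mean 0.1 × 1.272 / 0.9 = 0.14 SD. That is the bias left in a raw t-test.

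**Precision, random 20% loss in one arm.**
- Raw t-test: SE = √(1/24 + 1/30) = 0.274.
- Change t-test: 0.274 × √(2 × (1 − 0.7)) = 0.212.
- Baseline-adjusted: 0.274 × √(1 − 0.7²) = 0.196; simulated 0.199, since the slope must be estimated.
- All-visit model: simulated 0.196.

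Baseline adjustment against raw: 1 − 0.199/0.274 = 27% to 1 − 0.196/0.274 = 28%. Against change: 1 − 0.199/0.212 = 6% to about 8%. All visits against baseline adjustment: 1 − 0.196/0.199 = 1.5%. For an assumed 0.5 SD difference, power = Φ(0.5/SE − 1.96): 45% (raw), 65% (change), 71% (baseline-adjusted), 72% (all visits).

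**The case against.** The strongest reply is about size. A bias of 0.25 SD requires the very lowest-ranked men to leave one arm and nobody to leave the other. Graded selection roughly halves it or more. On a change-score reading, which section 11 permits, that scenario gives no bias at all. This stands, and the larger figure should be read as the extreme of that loss pattern at correlation 0.7, not as an expectation. The 28% gain in precision likewise applies only against a raw-value test.

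The mechanism can also be questioned. Section 10 lists itching, dryness and headache, and nothing ties these to diameter. Loss of poor responders looks more like men choosing to leave, and those who withdraw consent cannot be kept in follow-up. This stands too: continued measurement reduces bias but does not remove it.

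It can also be said that a baseline-adjusted week-36 comparison would serve almost as well as a model of all visits. On precision that is right. On bias the model helps under strong selection on values already seen, and little under graded selection.

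Some stronger readings are tempting but unsupported. A reader might infer that any adverse event ends participation; 4.3 requires the investigator's judgement on both risk and interest. A reader might also infer that the result will be biased towards the herbal arm; the documents support neither a direction nor a size.

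**Conclusion.** The gap in the text is clear. Section 4.3 ends follow-up together with participation, and section 11 gives hair diameter plain t-tests without baseline adjustment, a stated visit, a stated scale or an as-randomised analysis set. The consequence is conditional: bias arises only if outcome-related loss differs between arms, which the documents neither show nor exclude. On the assumed inputs it runs from zero to about 0.25 SD for selection on diameter already seen. It is about 0.14 SD for a change-score test if the poorest changers leave, and larger (0.32 SD, raw test) if loss follows values not yet seen. The precision gain from baseline adjustment does not depend on dropout: substantial against a raw test, modest against a change score. The plan should be changed because the remedy is cheap, not because serious bias has been demonstrated. Confidence is medium. The consent form was not available and is not judged.

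**What to change.** 1. In section 4.3, separate stopping study treatment from leaving follow-up. Men who stop treatment are still measured at the visits already scheduled, unless they withdraw consent or are withdrawn from the visits. The rules for stopping treatment stay as they are.
2. In section 11, make the main result the week-36 between-arm difference adjusted for baseline diameter, with all randomised men analysed in their assigned arm. Section 11 names no visit; week 36 is the end of treatment in section 2. A repeated-measures model (baseline diameter, arm, visit, arm-by-visit) using every available visit is a suitable way to do this, because it keeps the earlier values of men later lost. SPSS, the planned software, can fit it.
3. Report losses by arm, visit and reason, including men who withdrew consent.

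The cost is a few lines of text, attendance of men off treatment at existing visits, and slightly more analysis.
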